#### **7.1.3 Therapeutic response (Overall Clinical Outcome + Microbiological Outcome)**

1. Therapeutic cure: TSSS (otalgia+edema+otorrhea) of “0” and bacteriological response eradication or presumed eradication.
2. Therapeutic failure:
  - Positive culture for pathogen or,
  - negative culture or presumed eradication with TSSS  
(otalgia+edema+otorrhea)>0

Overall Clinical Outcome + Microbiological Outcome will be determined for each patient for Visit 3 and at Visit 4 after microbiological culture results are made available to the Sponsor or designee.

#### **7.1.4 Primary Efficacy Endpoint**

Based on the definitions in Sections 7.1.3, the primary efficacy endpoint will be the proportion of patients with Therapeutic cure at Visit 3 in the MITT\_PA/SA population (pathogen positive subset of the CITT population which includes all patients who received study medication and had culture positive for *P. aeruginosa* and/or *S. aureus* at baseline in the evaluable ear).

#### **7.1.5 Secondary Efficacy Endpoints**

Based on the definitions in Sections 7.1.1 and 7.1.3, the secondary efficacy endpoints will be:

##### Principal secondary endpoint:

- Time to end of ear pain.

End of ear pain is defined as the interval between the first dose of study medication and the first day (morning or evening) on which there is no use of analgesics, the diary pain score is zero and the score remains at zero for all subsequent visits (until end of the study)

This time will be calculated on the basis of the patient diary entries.

##### Other secondary endpoints:

- Sustained microbiological cure
- Clinical cure at Visit 3 and Visit 4
- Microbiological success at Visit 3 and Visit 4
- Therapeutic cure (clinical cure +microbiological cure) at Visit 4
- Changes in Brighton grading at Visit 3 and Visit 4
- Changes in otorrhea at Visit 3 and Visit 4
- Changes in edema at Visit 3 and Visit 4
- Changes in otalgia assessed by the investigator at Visit 3 and Visit 4

## 7.2 Safety Parameters

Safety will be assessed by AEs and vital signs. In addition, a urine pregnancy test for females of childbearing potential will be performed at Visit 1.

### 7.2.1 *Adverse Events*

#### 7.2.1.1 *Definitions*

An adverse event (AE) is any untoward medical event that occurs in a patient or subject who has received an investigational product, and does not necessarily have a causal relationship with this treatment. An AE can therefore be any unfavorable and unintended sign (including abnormal laboratory finding), symptom, or disease temporally associated with the use of an investigational product, whether or not related to the product.

An illness present at entry to the study is considered a pre-existing condition and will not be considered an AE. However, if a pre-existing condition worsens during the study, this may be considered an AE. Pre-existing conditions will be documented in the EDC. If pre-existing signs and symptoms of AOE (otalgia, edema and otorrhea) worsen during the study, this will be considered a treatment failure instead of an AE. If a patient has unilateral AOE at baseline and it becomes bilateral during the study, then the AOE in the contralateral ear will not be considered as an adverse event. All AEs, including intercurrent illnesses, that occur during the study (i.e., between study enrollment and Visit 4) must be reported and documented as described below.

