### 6.4 Blinding and Breaking the Blind

All study medication products (test and comparators) will have the same packaging and labels.

The boxes in which the study medication is packaged, shipped, and dispensed will be identical in appearance. When patients return their used and unused study medication containers to the study site, they will be encouraged to bring them in the original cartons.

Microbiological samples will be processed by a central laboratory under blinded conditions. The central laboratory will be blinded to the treatment assignment of the patient from whom the sample was taken.

Unblinding of study treatment assignment should be an unusual occurrence, and should be done only in case of an emergency when knowledge of the actual treatment becomes medically necessary to affect treatment options. For example, if a patient is worsening, especially if there are worsening systemic signs or symptoms, then, especially because one of the treatment arms does not contain an antibiotic, it may be important to know if treatment with a topical and/or systemic antibiotic might be a reasonable treatment option. The investigator will be able to unblind the study treatment at any time through IWRS.

The treatment unblinding information will be accessible by right-clicking the patient in the "List of patients" tab. A first message will inform the investigator of the unblinding instructions to follow. In order to complete the unblinding process, the following information will be required: the user's password, the patient code concerned by the unblinding request, the patient's birth date and the reason for unblinding.

In this way, the only person unblinded will be the investigator. The investigator should only share this information with people who need to know for the further treatment of the patient and should not be shared with SALVAT or [REDACTED]'s personnel.

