#### 7.2.1.2 *Assessment of Adverse Event*

Volunteered, observed, and elicited AEs will be recorded. This includes AEs the patient reports spontaneously, those the Investigator observes, and those elicited in response to questions from the study staff. Patients will be asked open-ended questions, such as "How have you been feeling since your last visit?", at each study visit. If a patient or patient's caregiver reports any pain or illness during or after administration of the eardrops (i.e. itching), the pain or illness experienced by the patient should be recorded as an AE.

Each AE will be assessed by the Investigator with regard to the following categories.

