#### 7.2.1.2.1 *Serious Adverse Event*

International Conference on Harmonization (ICH) Guidelines and federal regulations define a serious adverse event (SAE) as any untoward medical occurrence that at any dose:

- Results in death;
- Is life-threatening. This means that the patient is at risk of death at the time of the event; it does not mean that the event hypothetically might have caused death if it were more severe;
- Requires or prolongs patient hospitalization;
- Results in persistent or significant disability or incapacity; or

- Is a congenital anomaly or birth defect.

Important medical events that may not be immediately life-threatening or result in death or hospitalization but that may jeopardize the patient or require intervention to prevent one of the above outcomes usually should also be considered serious.

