#### 7.2.1.4 Reporting Serious Adverse Events

The Investigator must report any SAE that occurs during the study (i.e., between study entry and Visit 4), regardless of relationship to study medication, to [REDACTED] [REDACTED] within 24 hours of discovering the event. In addition, if the investigator learns of an SAE occurring after the last follow-up visit, but within 30 days after the last administration of the study drug, he/she should immediately report the event to the Safety Officer at [REDACTED].

Directions for reporting an SAE appear below.

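### Protocol 7.2.1.1 takes worsening ear pain, swelling or discharge, and new contralateral AOE, out of adverse events with no exception for serious cases, which contradicts the SAE definition and reporting duty in 7.2.1.2.1 and 7.2.1.4

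*Protocol*

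**What the plan says.** Protocol 7.2.1.1 starts from a general rule on illness present at entry: "if a pre-existing condition worsens during the study, this may be considered an AE". It then makes two exclusions for the disease under study.

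- **Worsening.** "If pre-existing signs and symptoms of AOE (otalgia, edema and otorrhea) worsen during the study", the protocol says, "this will be considered a treatment failure instead of an AE".
- **The other ear.** Where disease is unilateral at baseline and becomes bilateral, "then the AOE in the contralateral ear will not be considered as an adverse event". Section 8.2.2 repeats this and sends the information to the comments and resupply pages of the EDC.

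The provisions on seriousness follow.

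- Section 7.2.1.2: "Each AE will be assessed by the Investigator with regard to the following categories". Seriousness (7.2.1.2.1) is the first of those categories.
- Section 7.2.1.2.1 defines an SAE as an untoward medical occurrence with one of several listed outcomes. One is "Requires or prolongs patient hospitalization". The disease under study is not excluded.
- Section 7.2.1.3 has the seriousness classification entered with the event on the Adverse Events page.
- Section 7.2.1.4: "The Investigator must report any SAE that occurs during the study", whatever its relationship to study medication and within 24 hours of discovery.

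Protocol 10.1.11 and SAP 4.8 build the safety outputs from adverse events and vital signs, with exposure added in the SAP. SAP 4.8.2 counts events that worsen after dosing as treatment-emergent. It neither repeats the exclusions in 7.2.1.1 nor says how serious worsening of AOE is handled.

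**The concern.** Treating ordinary non-response as an efficacy outcome is common and reasonable. The difficulty is that the exclusion is written without a seriousness limit. A patient admitted to hospital because ear pain or canal swelling worsened is not an adverse event under one section and a 24-hour reportable SAE under two others. No sentence in either document says which prevails.

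The SAE route carries more than a line in a table. Sponsor review and possible action on the study (7.2.1.4), follow-up until the event resolves or is judged chronic or stable (7.2.1.5), and IRB or IEC reporting of related SAEs (7.2.1.6) all run through it. A patient taken off study medication for lack of improvement after Visit 2 is withdrawn and recorded as a treatment failure (8.2.2), and withdrawn patients are excepted from Visit 4 (8.2.4). For such a patient the SAE route may be the main safety follow-up left.

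**Working it through.** The point rests on the text. The plan states no figure to reproduce.

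**Step 1. Follow four cases through the sections.**

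| Case | Under 7.2.1.1 | Under 7.2.1.2.1 and 7.2.1.4 | Agree? |
|---|---|---|---|
| Hospitalized for worse otalgia, edema or otorrhea in the study ear | Treatment failure, not an AE | SAE, report within 24 hours | No |
| Hospitalized for new AOE in the other ear | Not an AE | SAE, report within 24 hours | No |
| New complication (perichondritis, systemic illness) that meets a seriousness criterion | Not named in either exclusion, so the general AE definition applies | SAE, report within 24 hours | Yes |
| Worse pain or discharge that meets no seriousness criterion | Treatment failure, not an AE | Not an SAE | Yes |

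The contradiction is confined to the first two rows.

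**Step 2. See whether a later step recovers those two rows.**

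- Section 7.2.1.2 applies the seriousness assessment to adverse events, and 7.2.1.2.1 is numbered beneath it. An occurrence already classed as something other than an AE does not reach that assessment on a literal reading.
- Section 7.2.1.3 puts the seriousness field on the Adverse Events page, which would not be opened.
- SAP 4.8.2 works on recorded events, so it cannot restore one that was never entered.
- Treatment failures and rescue use are tabulated under SAP 4.5.3 and 4.7, but with no seriousness flag.
- Section 7.2.1.4 still requires every SAE to be reported. This is the one route left, and it depends on the site reading it as overriding 7.2.1.1.

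**Step 3. A related overlap.** Section 7.2.1.2 asks for pain during or after instillation to be recorded as an AE. Worsening otalgia in the study ear after a dose fits both that sentence and the exclusion in 7.2.1.1, and the text does not separate them.

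**Step 4. Scale, on assumed rates only.** Inputs: 500 randomized at 2:2:1 (Protocol synopsis), so 500 × 2/5 = 200, 200 and 500 × 1/5 = 100. The documents give no rate *p* of serious worsening within the exclusion, so *p* is assumed. The expected count is *n* × *p*, and the chance of at least one case is 1 − (1 − *p*)^*n*.

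| Assumed *p* | *n* = 100: expected; chance of at least one | *n* = 200: expected; chance of at least one |
|---|---|---|
| 0.5% | 0.5; 39% | 1; 63% |
| 1% | 1; 63% | 2; 87% |
| 2% | 2; 87% | 4; 98% |
| 5% | 5; 99% | 10; over 99% |

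These figures show only what each assumption would imply. The one SAE in the sponsor's earlier 590-subject AOE study (Protocol 2.3) was a perichondritis, which lies outside the exclusion, so it cannot be used to estimate *p*.

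**The case against.** The strongest reply is that the sections can be read together: 7.2.1.1 classifies efficacy, while 7.2.1.2.1 and 7.2.1.4 govern serious events. The SAE definition does not exclude the study disease, and the instructions in 7.2.1.4 send a form straight to the safety center without making that depend on an EDC page. Section 7.2.1.6 separately requires unanticipated problems, including any death, to go to the IRB or IEC. This stands to the extent that concealment is not established. It does not remove the contradiction, because a site that follows 7.2.1.1 as written has a textual reason not to report.

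It is also fair that worsening stays visible by arm. SAP 4.3.1, 4.5.3, 4.7.3 and 4.8.4.1 tabulate discontinuations by reason, rescue use, clinical outcome, every Brighton grade, and vital signs including temperature. None of these identifies which cases were serious.

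Three stronger readings are tempting, and the documents do not support them.

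- **That all worsening of AOE is removed from safety reporting.** The exclusion names three signs and symptoms plus contralateral AOE. Systemic signs and perichondritis are not among them.
- **That the fluocinolone-only arm is the most affected.** Section 6.4 discusses unblinding a patient who worsens, "especially because one of the treatment arms does not contain an antibiotic", and SAP 1 expects both comparators to be less effective. That makes the inference plausible. But the systemic signs stressed in 6.4 fall outside the exclusion, no rate is given, and the earlier study had no fluocinolone-only arm. With half the patients of each other arm, this arm would have the largest count only if its rate were more than twice theirs.
- **That the safety comparison is tilted toward the sponsor's product.** If the comparators are less effective, as the plan expects, undercounting serious worsening would flatter the comparators.

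**Conclusion.** The contradiction holds. For two kinds of event, worsening of the three named signs and symptoms and new contralateral AOE, 7.2.1.1 points away from adverse-event recording while 7.2.1.2.1 and 7.2.1.4 require an SAE report when a seriousness criterion is met. Nothing else in the Protocol or SAP resolves it. Such an event can, but not necessarily will, go unreported and be absent from the safety tables.

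The size is unknown. Entry is limited to uncomplicated disease of Brighton grade II or III, so few cases are likely. The consequence is for individual safety reporting. The primary endpoint, sample size and efficacy analyses are unaffected. The conclusion assumes that a site may apply 7.2.1.1 literally, and that no site training or EDC instruction outside these documents already settles the matter.

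**What to change.** Amend 7.2.1.1 to state that worsening of AOE, or new AOE in the contralateral ear, that meets any criterion in 7.2.1.2.1 is also recorded on the Adverse Events page and reported as an SAE under 7.2.1.4. Keep the treatment-failure classification for efficacy. Align three other places:

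- **Protocol 8.2.2:** make the contralateral-AOE sentence subject to the same exception.
- **Protocol 7.2.1.2:** say how pain during or after the drops is told apart from worsening otalgia.
- **SAP 4.8.2:** state that these events enter the SAE and treatment-emergent tables.

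A note to sites should go with the change. Section 11.4 reserves unapproved administrative changes for minor ones that leave the benefit/risk ratio untouched, so this is best handled as a formal amendment with IRB/IEC approval. The cost is that paperwork and a few SAE reports that overlap with efficacy failures.

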#### 7.2.1.2 *Assessment of Adverse Event*

Volunteered, observed, and elicited AEs will be recorded. This includes AEs the patient reports spontaneously, those the Investigator observes, and those elicited in response to questions from the study staff. Patients will be asked open-ended questions, such as "How have you been feeling since your last visit?", at each study visit. If a patient or patient's caregiver reports any pain or illness during or after administration of the eardrops (i.e. itching), the pain or illness experienced by the patient should be recorded as an AE.

Each AE will be assessed by the Investigator with regard to the following categories.

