## 5. STUDY POPULATION

### 5.1 Inclusion Criteria

1. Male or female, at least 6 months of age;
2. Patients with diagnosis of uncomplicated acute diffuse otitis externa of less than 21 days (3 weeks) duration, with a total symptom score of at least 5 as defined under Efficacy Parameters, in at least 1 ear. The individual symptom scores, as defined in Sections 7.1.1.1, 7.1.1.3, and 7.1.1.4, must be:
  - Otalgia: at least 2 (moderate or severe);
  - Edema: at least 2 (moderate or severe);
  - Otorrhea: at least 1 (mild, moderate or severe), with sufficient quantity of otorrhea to allow culture.
3. Patients with Brighton grading of II or III in at least 1 ear, as defined in Appendix 2.
4. Patients with otorrhea of sufficient volume for sampling for microbiological culture (sample must be taken at baseline visit prior to the first study dose).
5. Willingness to refrain from swimming through end of the study.
6. For adult patients, ability to understand and provide written informed consent  
For pediatric patients, signed informed consent from patient's legally authorized representative; also, if the patient is capable of providing assent, signed assent from the patient as applicable according to local regulations.
7. Females who are not pregnant, not lactating and are not planning a pregnancy. All females of childbearing potential (those who are not premenstrual, not postmenopausal or not surgically sterile) will be able to participate only if they have a negative urine pregnancy test prior to randomization, and if they agree to use adequate birth control methods to prevent pregnancy throughout the study.  
Adequate birth control methods included topical, hormonal-oral, implantable or injectable contraceptives; mechanical-spermicide in conjunction with a barrier such as condom or diaphragm; intrauterine device (IUD); or surgical sterilization of partner (must be  $\geq$  6 months post vasectomy). For non-sexually active females, abstinence was regarded as an adequate method of birth control; however, if the patient became sexually active during the study, she must have agreed to use adequate birth control methods as defined above for the remainder of the study.

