### 6.2 Administration

Study medication will be self-administered by the patient or administered by the patient's caregiver. At Visit 1, a study staff member will instruct the patient or caregiver in how to open the vials and administer study medication, and will supervise the patient or caregiver during administration of the first dose.

The method of administration for the investigational medication and the comparator medication will be the same: instillation of one vial in the affected ear canal(s) twice a day (approximately every 12h, morning and evening) for 7 consecutive days. Ear wicks or sponges may be used at the Investigator's discretion. Use of ear wicks or sponges must be documented in the EDC.

Study medication will be supplied in single-dose vials containing 0.25 mL deliverable volume per vial. A patient kit will contain 1 pouch of 14 blue translucent vials (2 strips of 7 vials). Patients with bilateral otitis externa will receive 2 kits. The patient or caregiver will administer the contents of 1 vial, twice daily to the affected ear(s) for seven days. The Ciprofloxacin and/or Fluocinolone acetonide dosage will be the same for patients of all ages. Each vial will be an intact unit, and the caregiver will twist off the top of the vial to administer the study medication. The solution should be warmed by holding the vial in the hand for one or two minutes to avoid dizziness which may result from the instillation of a

cold solution. The patient should lie with the affected ear upward, and then the medication should be instilled. The outer ear lobe should then be gently pulled upward and outward. This will allow the ear drops to flow down into the ear canal. This position should be maintained for 1 minute. Repeat, if necessary, for the opposite ear.

The planned maximum exposure to the active ingredient is approximately 1.5 mg of Ciprofloxacin and 0.125 mg of Fluocinolone acetonide per day (approximately 10.5 mg of Ciprofloxacin and 0.875 mg of Fluocinolone acetonide over a 7-day period). This quantity will be twice as much in case of bilateral disease.

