##### 7.1.1.2 *Pain (Otalgia)*

Otalgia in both ears will be assessed at Visits 1, 3, and 4. The investigator will ask the patient (or caregiver if patient is too young) to assess his or her level of pain on the day of the visit. If the patient has taken analgesic medication, he or she will be asked to assess the level of pain before taking the analgesic. For consistency, the assessment of otalgia should always be performed before the ear is examined. Assessments will be on the scale described in Blanch 2000. Otalgia will be assessed as:

- Severe (3) if it interferes with activities of daily living;
- Moderate (2) if it causes discomfort but does not interfere with activities of daily living;
- Mild (1) if there is awareness of pain but not much discomfort
- Absent (0) if there is total absence of pain.

At Visits 3 and 4, pain will be considered resolved if the pain level is 0. Otalgia will be considered improved if the pain level is lower than in the previous visit.

Moreover, patients will complete a diary twice daily in which they will record assessments of ear pain, pain medication use.

Throughout the study, patient or caregiver should record pain severity at least twice daily (prior to dosing). For patients under 7 years old, caregiver will complete the FLACC scale. Patients from 7 years old to younger than 13 years old will record the pain using the Wong Baker Faces Pain Scale. And patients 13 years old and older will record the pain using a VAS scale (see Appendix 3).

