4.8.2 Adverse Events

Adverse events will be coded using the MedDRA Version 20.0. Adverse events will be tabulated by body system, preferred term, and treatment group.

Treatment-emergent adverse events (TEAEs) will be tabulated for the following subsets:

1. All TEAEs;
2. Related TEAEs;
3. Serious adverse events (SAEs);
4. Related Serious TEAEs;
5. Adverse events leading to study discontinuation;
6. Adverse events leading to discontinuation of study medication;
7. Adverse events resulting in death;

Tabulations of AEs by body system, preferred term, treatment group, and severity, and by body system, preferred term, treatment group, and relationship to study medication will also be provided.

The data will be displayed as number of subjects experiencing the AE, percentage of subjects, and number of AEs. All AE summaries will provide the number of patients reporting at least 1 AE and the total number of events reported.

General Rules for Adverse Events

1. An AE will be considered as treatment-emergent if it begins on or after the first study drug dosing or that worsens in severity after at least 1 dose of study drug has been administered. In case of insufficient information to determine if the event occurred before, during or after study drug dosing, the AE will be considered as treatment-emergent.

The imputation method for the handling of missing or partial dates will be as follows:

Start dates

- If the day is missing, but month and year are present and the same as the month and year of the first dose of study drug, then day will be set to the same day as the start of study drug. Otherwise, this will be imputed as the first day of the month.
- If the month is missing, but year is present and the same as the year of the first dose of study drug, then month will be set to the same month as the start of study drug. Otherwise, this will be imputed as January.
- If the year is missing, the event will be considered as treatment emergent and the start date will be imputed as the date of first treatment.

Stop dates

- If the day is missing, this will be imputed as the last day of the month, or the last day of participation in the study if the AE end month is the same as the last date of participation in the study.
- If the month is missing, this will be imputed as December, or the last month of participation in the study if the AE end year is the same as the last date of participation in the study

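### Pain in the treated ear that starts or rises when the drops go in is an adverse event under Protocol 7.2.1.2 but a treatment failure and not an adverse event under 7.2.1.1, so the ear-pain part of the tolerability comparison depends on which rule a site follows.

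*Protocol*

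**What the plan says.** Protocol 7.2.1.1 (Definitions) has two relevant rules. On baseline disease: "An illness present at entry to the study is considered a pre-existing condition and will not be considered an AE". On the symptoms of acute otitis externa (AOE) itself, with otalgia named, it says that if they "worsen during the study, this will be considered a treatment failure instead of an AE".

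Protocol 7.2.1.2 (Assessment of Adverse Event) covers the case where a patient or caregiver "reports any pain or illness during or after administration of the eardrops (i.e. itching". Its instruction is that "the pain or illness experienced by the patient should be recorded as an AE". It sets no time window, does not ask that the pain be new or worse, and makes no exception for otalgia of the treated ear.

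Entry requires ear pain in at least one ear: "Otalgia: at least 2 (moderate or severe" (Protocol 5.1, criterion 2). Dosing is "twice a day (approximately every 12h, morning and evening) for 7 consecutive days" (Protocol 6.2). In the diary, patients or caregivers "should record pain severity at least twice daily (prior to dosing" (Protocol 7.1.1.2). Protocol 7.2 names AEs and vital signs as the safety parameters, with no separate measure of tolerability at instillation.

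SAP 4.8.2 treats as treatment-emergent an AE that begins on or after first dosing or "worsens in severity after at least 1 dose of study drug has been administered". It has no rule for otalgia.

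**The concern.** The two sections give opposite instructions for one kind of event: pain in the treated ear that appears or increases when the drops are instilled. Because moderate or severe otalgia is an entry requirement, most such pain arises in an ear that already hurts, and a site can defensibly call it either worsened otalgia or a reaction to the drops.

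AEs are the only planned safety measure that could capture this pain. If a site applies the otalgia exception to all ear pain, pain caused by a study product never reaches the AE page. If a site applies 7.2.1.2 literally, pain from disease that is not yet cured is recorded as an AE, and an arm with lower efficacy then tends to collect more of them. In both cases the ear-pain line of the AE table reflects the recording rule as well as the product.

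**Working it through.** No planned figure depends on this, so there is nothing in the plan to reproduce. The check sets the passages side by side and then adds an illustration on assumed rates.

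**Step 1: how each section classifies pain in the treated ear.**

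| Event | 7.2.1.1 | 7.2.1.2 |
|---|---|---|
| Otalgia unchanged since entry | Pre-existing, not an AE | AE if the sentence is read alone; excluded if 7.2.1.1 governs it |
| Otalgia worse as part of AOE | Treatment failure, not an AE | AE if reported after a dose |
| Pain that starts or rises on instillation | Treatment failure, not an AE, if read as worsened otalgia | AE |
| Itching, stinging or another new local symptom | Not among the symptoms excepted, so an AE | AE |

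The second and third rows conflict. With doses about 12 hours apart for 7 days, all treatment-period pain after the first dose comes after an administration, so the timing words in 7.2.1.2 do not separate the two rows.

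**Step 2: whether anything downstream resolves it.**

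- The treatment-emergent rule in SAP 4.8.2 sorts events already recorded. It cannot restore an event kept off the AE page.
- The blinded review in SAP 4.5.3 decides types of pain treatment, rescue medication and effective concomitant therapy. The one in SAP 4.3.2 decides major deviations and analysis sets. Neither is assigned ear-pain AEs.
- Causality and onset time (Protocol 7.2.1.2.3 and 7.2.1.3) are collected only for recorded AEs.
- The diary score is scheduled before each dose, so it does not isolate pain at instillation.

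**Step 3: illustration. All rates are assumed, because the documents give none.** Let i be the proportion with instillation pain (2% to 5%, the same in each arm), w the proportion with worsened otalgia, counted as separate patients, and s the share of patients at sites that record both under 7.2.1.2. The other sites apply the otalgia exception to all ear pain and record none.

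Recorded ear-pain AE rate = s × (i + w)

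With w = 5% in every arm:

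- s = 0: 0%
- s = 0.5: 0.5 × (2% + 5%) = 3.5%, to 0.5 × (5% + 5%) = 5%
- s = 1: 2% + 5% = 7%, to 5% + 5% = 10%

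With w = 5%, 8% and 15% on the combination, ciprofloxacin and fluocinolone:

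| s | Combination | Ciprofloxacin | Fluocinolone |
|---|---|---|---|
| 0 | 0% | 0% | 0% |
| 0.5 | 3.5–5% | 5–6.5% | 8.5–10% |
| 1 | 7–10% | 10–13% | 17–20% |

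Instillation pain was set equal across arms, so a count of instillation pain alone would give 2% to 5% in each. The differences from the combination at s = 1, 3 points for ciprofloxacin (8 − 5) and 10 points for fluocinolone (15 − 5), come entirely from worsened disease.

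**The case against.** The strongest reply is that the sections can be read in sequence. Section 7.2.1.1 defines an AE and closes by directing that AEs be documented as the text below it describes; 7.2.1.2 then says how they are elicited. On that reading unchanged baseline otalgia is already excluded, 7.2.1.2 is about reactions to the drops (its example is itching), and 7.2.1.1 is about the course of the disease. This stands for unchanged pain. It does not settle pain that rises on instillation, because no criterion separates that from worsened otalgia and nothing says which section prevails.

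Causality grading is a second reply. Disease pain logged as an AE can be rated not related and so stay out of the related-event tables. This answers part of the worry about literal use of 7.2.1.2, although the tables of all AEs would still contain it. It does nothing for events never recorded.

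Third, safety has no formal testing (SAP 4.7.1.2), and allocation is randomized and double-blind, so differing site practice does not by itself favour an arm. Both stand. Blinding does not, however, stop residual pain from differing by arm when efficacy differs.

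Fourth, the AEs that Protocol 2.3 lists for the sponsor's earlier AOE trial of 590 subjects include no ear pain or itching. The documents therefore give no reason to expect a high rate, and no rate to use.

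A reader might also infer that a mix of practice across about 50 sites reverses the comparison. Suppose true instillation pain of 5% on the combination and 2% on ciprofloxacin, with residual disease pain in 40% and 60% (all assumed). Full use of 7.2.1.2 gives 1 − 0.95 × 0.60 = 43.0% against 1 − 0.98 × 0.40 = 60.8%. If half the patients are at sites that record none, the rates are 21.5% and 30.4%. The ratio is 0.71 both times, so the reversal comes from the assumed 40% against 60% and not from the mixture.

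**Conclusion.** The contradiction is real and narrow. For treated-ear pain that starts or rises on instillation, two adjacent sections give opposite recording instructions, and nothing in the protocol or SAP resolves it. The ear-pain part of the tolerability comparison therefore depends on site practice.

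Its size cannot be derived from the documents. The illustration shows only the mechanism: on its assumptions the combination's recorded rate runs from 0% to 10% according to the rule used, and differences between arms can reflect efficacy alone.

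Three stronger readings are tempting and not supported:

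- That local tolerability as a whole cannot be read. Itching and other new local reactions are AEs under both sections.
- That ear-pain AEs could be forecast anywhere from none to nearly all patients. The upper end needs unchanged baseline pain to be counted, which the definition in 7.2.1.1 naturally excludes.
- That efficacy endpoints are affected. Therapeutic cure rests on the symptom score and bacteriological response at Visit 3, with stated failure rules for missing data, rescue medication and discontinuation for lack of efficacy. SAP 4.7.3 censors time to end of ear pain at 17 days for treatment failures, but the documents do not say that the failure label in 7.2.1.1 feeds that rule.

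The sponsor should correct this, since ear pain from an ear drop is a natural safety question and the change is small. The primary efficacy test does not depend on it.

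**What to change.** Reconcile Protocol 7.2.1.1 and 7.2.1.2 with a cross-reference in each and one explicit criterion based on onset relative to instillation:

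- A new local symptom, or ear pain that the patient or caregiver reports as starting or increasing on instillation, is recorded as an AE despite the otalgia exception.
- Otalgia that persists or worsens as part of AOE is recorded as efficacy only.

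Add a matching line to SAP 4.8.2 so that the AE tables follow the same division.

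The criterion should not be a rise above the pre-dose diary score. No post-dose score is scheduled for comparison, and the diary uses three age-specific scales, so a threshold would have to be defined for each.

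The cost is about two protocol sentences, one SAP line and a line in site training. The change concerns AE recording only and leaves patient management as it is. The downside is slightly more judgement at the site when classifying pain.
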